**C35b. If drgbngevr= "yes": In the last month, did you go on a run or a binge? [bngm1]**

Yes

No

DK/R

*Interviewer prompt: Some other countries have Supervised Consumption Rooms, which are places where people can legally bring their own drugs, get supplies like clean needles, and use their drugs in*

Page 32 of 144

Brown University IRB Original Approval: 04/18/2019

Brown University IRB Amendment Approval: 11/22/2020

Brown University IRB Amendment Approval: 08/10/2020

Brown University IRB Amendment Approval: 10/15/2020

Brown University IRB Amendment Approval: 02/26/2021

Brown University IRB Continuing Review Approval: 03/18/2021

Brown University IRB Amendment Approval: 06/15/2021

Brown University IRB Amendment Approval: 09/01/2021

Brown University IRB Amendment Approval: 10/05/2021

Brown University IRB Amendment Approval: 10/15/2020

Brown University IRB Amendment Approval: 02/26/2021

Brown University IRB Continuing Review Approval: 03/18/2021

Brown University IRB Amendment Approval: 06/15/2021

Brown University IRB Amendment Approval: 09/01/2021

Brown University IRB Amendment Approval: 10/05/2021

BROWN

School of Public Health

Brown University IRB Amendment Approval: 11/09/2021

Brown University IRB Amendment Approval: 12/13/2021

front of staff in case they overdose. There are no places like this in the US. If there was a legal service you could go to for free to use drugs safely indoors...

**C36. Would you use this service? [sifuse]**

- Yes
- No
- DK/ R

**C37. If sifuse= "yes": How often do you think you would use this service? [siftimes]**

- Once or a couple of times
- About once a month
- At least every week
- Every day
- DK/ R

**C38. If sifuse= "yes": What is the longest time you would be willing to travel to use this service? [siftra]**

- 1-5 minutes
- 6-10 minutes
- 11-20 minutes
- 21-30 minutes
- More than 30 minutes
- DK/R [DK]

**C39. If sifuse= "yes": When would you be most likely to use this service? (Read out list; check all that apply) [sifpref]**

- Mornings, like 8am-12pm [1]
- Afternoons, like 12pm-4pm [2]
- Evening, like 4pm-8pm [3]
- Late evenings, like 8pm-12midnight [4]
- Other [77]
- DK/R [99]

**C39a. If sifpref= "other": When would you be most likely to use this service: \_\_\_\_\_**

**C40. Do you think that your friends (or other people you know) would use this service? [sifptp]**

- Yes
- No
- DK/ R

Revised & Approved 11/22/2019

Revised & Approved 12/09/2019

Administrative correction submitted 12/12/2019

Revised & Approved 08/17/2020

Revised and Approved: 10/15/2020

Revised and Approved 02/01/2021

Revised and Approved: 09/01/2021

*Interviewer prompt: We are now going to ask about drug dealing. By dealing, we mean giving drugs to someone in exchange for money, food, shelter, or other goods. Please remember that all responses are strictly confidential and will not be shared with anyone outside of the study team.*

**C41. Have you ever dealt drugs? [dealt]**

Yes

No

DK/R

**C42. If dealt= "yes": What is the main reason you've dealt drugs? (Read out list; check only one) [dealw]**

- Income for drugs
- Income for other purposes
- To clear debts
- For food or shelter
- Another reason

DK/R

**C42a. If dealw="another reason": What is the main reason you've dealt drugs: \_\_\_\_\_ [dealw\_oth]****C43. If dealt= "yes": In the last month, have you dealt drugs? [dealtm1]**

Yes

No

DK/R

**C44. If dealtm1= "yes": In the last month, have you dealt drugs that you suspected or knew had fentanyl in them? [fentdeal]**

Yes

No

DK/R

**C45. If dealt= "yes": Are you concerned about fentanyl contaminating your supply? [fentdeal\_concern]**

- Very concerned
- A little concerned
- Neutral
- Not concerned

DK/R

**C46. If dealt= "yes": If given the choice, would you prefer not to deal drugs that had fentanyl in them? [fentindrg]**

Page 34 of 144

Brown University IRB Original Approval: 04/18/2019

Brown University IRB Amendment Approval: 11/22/2020

Brown University IRB Amendment Approval: 08/10/2020

Brown University IRB Amendment Approval: 10/15/2020

Brown University IRB Amendment Approval: 02/26/2021

Brown University IRB Continuing Review Approval: 03/18/2021

Brown University IRB Amendment Approval: 06/15/2021

Brown University IRB Amendment Approval: 09/01/2021

Brown University IRB Amendment Approval: 10/05/2021

Brown University IRB Amendment Approval: 10/15/2020

Brown University IRB Amendment Approval: 02/26/2021

Brown University IRB Continuing Review Approval: 03/18/2021

Brown University IRB Amendment Approval: 06/15/2021

Brown University IRB Amendment Approval: 09/01/2021

Brown University IRB Amendment Approval: 10/05/2021

BROWN

School of Public Health

Brown University IRB Amendment Approval: 11/09/2021

Brown University IRB Amendment Approval: 12/13/2021

Very concerned  
 A little concerned  
 Neutral  
 Not concerned  
 DK/R

**C47. Has your drug use changed in any of the following ways because COVID-19? (Read out list; check all that apply) [cov\_use]**

- I use more (frequency or amount) than I did before [1]
- I use less (frequency or amount) than I did before [2]
- I use alone more often [3]
- I use alone less often [4]
- I use when naloxone is available more often [4]
- I use when naloxone is available less often [5]
- I taste or check drugs first more often [6]
- I taste or check drugs first less often [7]
- I have used different drugs because my normal supply has changed or dried up [8]
- I have started methadone, buprenorphine or some other form of treatment [9]
- I have stopped methadone, buprenorphine or some other form of treatment [10]
- I have changed how I have used drugs (for example you have switched from inhalation to injection) [11]
- No difference [12]
- Something else [77]
- DK/R [99]

**C47a. If covid\_use="77"; Is there something else that has changed about how you use drugs because of COVID-19? \_\_\_\_\_ [cov\_use\_oth]**

## **SECTION D: FENTANYL**

*Interviewer prompt: Now we are going to ask you questions about fentanyl. Please answer True, False, or Don't know/Refuse for the next 6 questions.*

**D1. Fentanyl is an opioid [info1]**

- True
- False
- DK/R

**D2. Fentanyl is not as strong as heroin [info2]**

- True
- False
- DK/R

**D3. Fentanyl acts more quickly than heroin [info3]**

- True
- False
- DK/R

**D4. Drugs that are mixed with fentanyl look different than drugs that are not mixed with fentanyl [info4]**

- True
- False
- DK/R

**D5. Someone is more likely to overdose when using drugs that contain fentanyl than when using drugs that do not contain with fentanyl [info5]**

- True
- False
- DK/R

**D6. In Rhode Island, fentanyl now causes more overdoses than heroin [info6]**

- True
- False
- DK/R

**D7. Have you ever been prescribed fentanyl by a doctor? [fentrx]**

- Yes
- No
- DK/R

**D8. If fentr= “yes”: In what forms have you been prescribed fentanyl? (Read out list; check all that apply) [fentform]**

- Skin patch [1]
- Pills [2]
- Nasal spray [3]
- Lozenge/lollipop [4]
- A film that dissolves under your tongue [5]
- A spray that goes under your tongue [6]
- Other: [7]
- DK/R [99]

**D8a. If fentform= “other”: In what forms have you been prescribed fentanyl: \_\_\_\_\_ [fentform\_oth]**

**D9. Have you ever used prescription fentanyl in a way that was not prescribed by a doctor (without a prescription, or different route or different dose than as prescribed by a doctor)? [fentnorx]**

- Yes
- No
- DK/R

**D10. If fentnorx= “yes”: In the last month, how often have you used prescription fentanyl in a way that was not prescribed by a doctor? [fentdiv6]**

- Never
- Once or a couple times
- At least every week
- Every day
- Multiple times per day
- DK/R

**D11. If fentnorx= “yes”: In the last month, what forms of prescription fentanyl have you used in a way that was not prescribed by a doctor? (Read out list; check all that apply) [fentdivform]**

- Skin patch [1]
- Pills (orally) [2]
- Nasal spray [3]
- Injecting [4]
- Snorting [5]
- Smoking [6]
- Lozenge/lollipop [7]
- A film that dissolves under your tongue [8]
- Other: [77]

Page 37 of 144

Brown University IRB Original Approval: 04/18/2019

Brown University IRB Amendment Approval: 11/22/2020

Brown University IRB Amendment Approval: 08/10/2020

Brown University IRB Amendment Approval: 10/15/2020

Brown University IRB Amendment Approval: 02/26/2021

Brown University IRB Continuing Review Approval: 03/18/2021

Brown University IRB Amendment Approval: 06/15/2021

Brown University IRB Amendment Approval: 09/01/2021

Brown University IRB Amendment Approval: 10/05/2021

Brown University IRB Amendment Approval: 10/15/2020

Brown University IRB Amendment Approval: 02/26/2021

Brown University IRB Continuing Review Approval: 03/18/2021

Brown University IRB Amendment Approval: 06/15/2021

Brown University IRB Amendment Approval: 09/01/2021

Brown University IRB Amendment Approval: 10/05/2021

BROWN

School of Public Health

Brown University IRB Amendment Approval: 11/09/2021

Brown University IRB Amendment Approval: 12/13/2021

DK/R [99]

**D11a.** If fentdivform= "other": In the last month, what forms of **prescription fentanyl** have you used in a way that was not prescribed by a doctor: \_\_\_\_\_ [fentdivform\_oth]

**D12.** If fentnorx= "yes": In the last month, how did you get fentanyl without a prescription?  
(Read out list; check all that apply) [fentbuy]

Purchased from a dealer or on the street [1]

A close friend [2]

A casual friend or acquaintance [3]

A sex partner [4]

An immediate family or household member [5]

An extended family member [6]

Purchased from the internet or "dark web" [7]

Other: [77]

DK/R [99]

**D12a.** If fentbuy= "other": In the last month, who did you get fentanyl without a prescription: \_\_\_\_\_ [fentbuy\_oth]

*Interviewer prompt: Now we are going to be talking about drugs that contained fentanyl. For example, you thought you were buying heroin, but it was contained fentanyl.*

**D13. I am confident that I have used a drug that contained fentanyl that was not sold as fentanyl.** [fentconfevr]

Strongly disagree	Disagree	Neutral	Agree	Strongly agree	DK/R
-------------------	----------	---------	-------	----------------	------

For responses *Strongly Disagree, Disagree, Neutral, DK/R* → skip to D19

**D14. In the last month, how often have you used fentanyl or drugs you were confident contained fentanyl?** [fentfreq]

Never

Once or a couple of times

About once a month

At least every week

Every day

DK/R

**D15. If fentfreq = "Once or a couple of times" or "About once a month" or "At least every week" or "Every day": What drugs have you used that you were confident contained fentanyl in the past... (Read out list; check all that apply) [fentconfevr]**

		Past month (Y/N)	Past 7 days (Y/N)	Past 3 days (Y/N)
D15a	Marijuana or hash oil, including edibles and synthetic marijuana			
D15b	Club drugs such as Molly, MDMA, Ecstasy, GHB, Ketamine OR Molly/MDMA/Ecstasy [MO]			
D15c	Psychedelics, such as Mushrooms, Acid, LSD, DMT OR Mushrooms [MU]			
D15d	Crystal methamphetamine (crystal meth, tina, crank, ice)			
D15e	Powder cocaine			
D15f	Crack cocaine			
D15h	Heroin			
D15j	Prescription Opioid Pills (Vicodin, Percocet, etc.)			
D15k	Prescription Benzodiazepines (Xanax, Klonopin, etc.)			
D15l	Prescription Stimulants (Adderall, Ritalin, etc.)			
D15m	Other:			

D15n	DK/R			
------	------	--	--	--

**D16. If fentfreq = "Once or a couple of times" or "About once a month" or "At least every week" or "Every day": The last time you used a drug you were confident contained fentanyl, did you know that the drug that contained fentanyl before you used it? [fentconf]**

Yes

No

DK/R

**D17. If fentfreq = "Once or a couple of times" or "About once a month" or "At least every week" or "Every day": The last time you used a drug you were confident contained fentanyl, why were you confident that it contained fentanyl? (Read out list, check all that apply) [fentwhy]**

A dealer told me [1]

A sex partner told me [2]

A friend told me [3]

I overdosed [4]

A sex partner overdosed [5]

A friend overdosed [6]

I had a bad reaction [7]

Quicker onset of high [8]

Different high [9]

Differences in appearance, smell or taste [10]

Other: [77]

DK/R [99]

**D17a. If fentwhy= "Other": The last time you used a drug you were confident contained fentanyl, why were you confident that it contained fentanyl: \_\_\_\_\_ [fentwhy\_oth]**

**D17a. If fentfreq = "Once or a couple of times" or "About once a month" or "At least every week" or "Every day": The last time you used a drug that you were confident contained fentanyl, how did you get it? [fentobt]**

Purchased from a dealer or on the street

A close friend

A casual friend or acquaintance

A sex partner

An immediate family or household member

An extended family member

Purchased from the internet or "dark web"

Other

DK/R

**D17b. If fentobt = "other": The last time you used a drug that you were confident contained fentanyl, how did you get it: \_\_\_\_\_ [fentobt\_why]**

**D18. If fentfreq = "Once or a couple of times" or "About once a month" or "At least every week" or "Every day": The last time you used a drug you were confident contained fentanyl, what did you do when you found out you? (Read list out loud; check all that apply) [skill1]**

- Took them as I usually would [1]
- Threw them out [2]
- Gave them away [3]
- Sold them [4]
- Went slower [5]
- Used less [6]
- Did a tester [7]
- Used with someone else around [8]
- Other: [77]
- DK/R [99]

**D18a. If skill1= "other": The last time you used a drug you were confident contained fentanyl, what did you do when you found out: \_\_\_\_\_ [skill1\_oth]**

*Interviewer prompt: Now that we have asked you what you've done in the past when you had drugs that contained fentanyl, we would like to know more about what you do in the future.*

**D19. What would you do if you found out your drugs had fentanyl in them? (Read list out loud; check all that apply) [motiv1]**

- Take them as I usually would [1]
- Throw them out [2]
- Give them away [3]
- Sell them [4]
- Go slower [5]
- Use less [6]
- Do a tester [7]
- Use with someone else around [8]
- Talk with the supplier or dealer [8]
- Other [77]
- DK/R [99]

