During the baseline visit, participants in both the experimental and control arms will be given a naloxone kit that includes two doses of intranasal naloxone along with a wallet card with information about fentanyl and the educational flyer in a discreet pouch or bag. At all other assessment visits participants will be referred to community locations for no-cost or low-cost naloxone access. We have created a flyer (see **Attachment B**) that provides specific information about locations where naloxone can be obtained, as well as a link to a page that contains this information on [www.PreventOverdoseRI.org](http://www.PreventOverdoseRI.org). In Rhode Island, naloxone is available via pharmacies and community organizations to anyone in the state via standing order authorized by [name] (RAPIDS co-investigator). Additionally, all participants will be asked to provide a urine sample for a 12-drug panel rapid urine screen plus fentanyl rapid urine screen (one sample) at each study visit. The urine screens are not meant to determine a participant's eligibility based on their self-reported drug use. The urine screens will measure fentanyl and other recent drug exposure among participants to determine if there was unintentional exposure to fentanyl. Once a urine screen is completed, the sample will be disposed of immediately. Finally, participants will be asked to provide dried blood spots at three study visits (i.e., baseline, 6 months and 12 months) to confirm results from urine screening in the 12-drug panel above, in addition to detection of novel synthetic opioid and other psychoactive substances. Testing of dried blood spots will be undertaken routinely throughout and at the end of the study, and will not be used to determine a participant's eligibility. After the samples have been analysed for the study endpoints as specified in the protocol, remaining samples will be stored for use in future Institutional Review Board approved substance use and infectious disease (e.g., HIV, hepatitis C, and COVID-19) related research. Additional consent will not be sought for this storage and future use.

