Consideration of Sex, Biological Variables, and Other Sociodemographic Characteristics: Participants will report their age, sex at birth, current gender identity, sexual orientation, race, ethnicity, educational attainment, employment status, and recent and lifetime experiences of housing instability and homelessness, involvement

with the criminal justice system, and participation in sex work.

Substance Use Experiences: Participants will report on recent and lifetime substance use patterns (i.e., age at first use, frequency of use, polysubstance use, binge use, social context of use, route of administration), and perceptions towards fentanyl (i.e., intentional use of fentanyl, suspected exposure to fentanyl-contaminated drugs). The questionnaire will also incorporate a number of standardized instruments, including the Addiction Severity-Index Lite (drug and alcohol section), and the Short Opiate Withdrawal Scale (SOWS).

Healthcare Utilization: Participants will report on health insurance status; prior mental health diagnoses, past treatment experiences, use of medications (buprenorphine, naltrexone, or methadone), and barriers to substance abuse treatment. We will administer a modified version of the Circumstances, Motivation, and Readiness (CMR) scale, which has been used to assess motivation to engage in substance use treatment.

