**C21d. Prescription stimulants such as Adderall, Ritalin, Focalin, Concerta, Dexedrine? \_\_\_\_\_ [m1pilij\_ps]**

**C22. Have you injected any of the following prescription drugs in the past 7 days or past 3 days? (Read out list and time increments) [daypilij]**

		Past 7 days (Y/N) [d7pilij]	Past 3 days (Y/N) [d3pilij]
C22a	Prescription opioids such as Percocet, OxyContin, Dillaudid, Vicodin		
C22b	Medications used for opioid use disorder such as Methadone, buprenorphine/Suboxone		
C22c	Benzodiazepines/Benzos such as Xanax, Ativan, Valium, Klonapin		
C22d	Prescription stimulants such as Adderall, Ritalin, Focalin, Concerta, Dexedrine		

**C23. Have you ever injected any of the following drugs? We will not be asking about fentanyl use right now. We will be asking about that separately later on. (Read out list and time increments) [EVDRGIJ]**

		Ever (Y/N) [All NO] → skip to C5
C23a	Club drugs such as Molly, MDMA, Ecstasy, GHB, Ketamine	[EvCD]
C23b	Psychedelics, such as Mushrooms, Acid, LSD, DMT	[EvP]
C23c	Crystal methamphetamine (crystal meth, glass, tina, crank, ice)	[EvCM]
C23d	Powder cocaine	[EvPC]
C23e	Crack cocaine	[EvCC]
C23f	Heroin	[EvHE]
C23g	Alcohol	[EvALC]
C23h	Other:	[EvOT]

**C24. How old were you when you injected any of the following drugs? We will not be asking about fentanyl use right now. We will be asking about that separately later on. (Read out list and time increments) [YRDRGIJ]**

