An immediate family or household member [5]

An extended family member [6]

Purchased from the internet or “dark web” [7]

Other: [77]

DK/R [99]

**C12a.** If *fentbuy\_fu*= “other”: **In the last month, who did you get fentanyl without a prescription:** \_\_\_\_\_ [*fentbuy\_oth\_fu*]

*Interviewer prompt: Now we are going to be talking about drugs that contained fentanyl. For example, you thought you were buying heroin, but it was contained fentanyl.*

**C13.** **In the last month, how often have you used fentanyl or drugs you were confident contained fentanyl?** [*fentfreq\_fu*]

Never

Once or a couple of times

About once a month

At least every week

Every day

DK/R

**C14.** If *fentfreq\_fu* <> “never” or “DK/R”: **What drugs have you used that you were confident contained fentanyl in the past... (Read out list; check all that apply)** [*fentdrgconf\_fu*]

		Past month (Y/N)	Past 7 days (Y/N)	Past 3 days (Y/N)

Page 100 of 144

Brown University IRB Original Approval: 04/18/2019

Brown University IRB Amendment Approval: 11/22/2020

Brown University IRB Amendment Approval: 08/10/2020

Brown University IRB Amendment Approval: 10/15/2020

Brown University IRB Amendment Approval: 02/26/2021

Brown University IRB Continuing Review Approval: 03/18/2021

Brown University IRB Amendment Approval: 06/15/2021

Brown University IRB Amendment Approval: 09/01/2021

Brown University IRB Amendment Approval: 10/05/2021

Brown University IRB Amendment Approval: 10/15/2020

Brown University IRB Amendment Approval: 02/26/2021

Brown University IRB Continuing Review Approval: 03/18/2021

Brown University IRB Amendment Approval: 06/15/2021

Brown University IRB Amendment Approval: 09/01/2021

Brown University IRB Amendment Approval: 10/05/2021

BROWN

School of Public Health

Brown University IRB Amendment Approval: 11/09/2021

Brown University IRB Amendment Approval: 12/13/2021

C14a	Marijuana or hash oil, including edibles and synthetic marijuana			
C14b	Club drugs such as Molly, MDMA, Ecstasy, GHB, Ketamine OR Molly/MDMA/Ecstasy [MO]			
C14c	Psychedelics, such as Mushrooms, Acid, LSD, DMT OR Mushrooms [MU]			
C14d	Crystal methamphetamine (crystal meth, tina, crank, ice)			
C14e	Powder cocaine			
C14f	Crack cocaine			
C14h	Heroin			
C14j	Prescription Opioid Pills (Vicodin, Percocet, etc.)			
C14k	Prescription Benzodiazepines (Xanax, Klonopin, etc.)			

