Determine whether intervention efficacy varies across participant subgroups (Aim 3). This is an exploratory aim. We will examine if heterogeneity of intervention effect is modified by key baseline characteristics of interest, including: age; sex; type, frequency, and route of drug use; baseline level of overdose risk (e.g., lifetime history of overdose); and pre-intervention motivations for fentanyl test strip utilization. We will perform stratified subgroup analyses to determine if treatment effects vary between groups of individuals.

---

 [10.1136/bmj.c2073](https://doi.org/10.1136/bmj.c2073)

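### The skip after baseline item D13 is narrower than the fentanyl-use items it controls, so some knowing fentanyl users are never asked D14 to D18

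*Protocol*

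**What the plan says.** **Baseline survey (Protocol, Attachment A, Section D).** D13 is an agreement item with no time window: "I am confident that I have used a drug that contained fentanyl that was not sold as fentanyl". The rule printed beneath it is "For responses *Strongly Disagree, Disagree, Neutral, DK/R* → skip to D19". The items passed over are:

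- D14 (fentfreq): past-month frequency of using fentanyl or drugs the person was confident contained it.
- D15: which drugs, in the past month, 7 days and 3 days.
- D16: prior knowledge, "did you know that the drug that contained fentanyl before you used it".
- D17 and its sub-items: why the person was confident, and how the drug was obtained.
- D18 (skill1): what the person did on finding out.

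D15 to D18 each carry their own condition that fentfreq shows some use.

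**Follow-up survey (Attachment A, Section C).** C13 puts the frequency question, "In the last month, how often have you used fentanyl or drugs you were confident contained fentanyl", with no D13-type gate before it. C18 (skill1_fu) is also printed without a condition.

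**Stated purposes.** Protocol 3.1b, under Substance Use Experiences, lists "intentional use of fentanyl, suspected exposure to fentanyl-contaminated drugs" among the things participants will report. Protocol 3.1a says the urine screens, done at each visit, are there to "determine if there was unintentional exposure to fentanyl". The Reopening Plan, in its justification for reopening the research space, says three-day drug use reported in the survey will be correlated with the urine result.

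**The concern.** The gate and the items behind it describe different populations. D13 is about fentanyl that arrived undisclosed, and the interviewer prompt just before it gives the example of a person who thought they were buying heroin. D14 is about any use of fentanyl. A person who buys fentanyl as fentanyl belongs in D14 but has no reason to agree with D13.

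Intentional use is one of the measures the protocol says it will collect, and it is what the urine result has to be set against. A urine screen shows exposure and says nothing about intent. If the self-report is missing for some of the people who use fentanyl on purpose, their positive screens cannot be told apart from those of people exposed without knowing it. The baseline value needed for any description of change in fentanyl use, or in the response to finding fentanyl, is missing for the same people.

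**Working it through.** No sample size, power or event count depends on this point. The check is a trace of the routing.

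**Step 1. Follow one participant through the baseline form.** Take someone who injects fentanyl bought as fentanyl, and who is not confident of ever having been sold it as something else.

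1. Section C injection items (C23 to C26): there is no fentanyl row, and the interviewer says "We will not be asking about fentanyl use right now. We will be asking about that separately later on".
2. D9, misuse of prescription fentanyl: No, so D10 to D12 do not apply.
3. D13: Disagree is the truthful answer, and the form jumps to D19.
4. D14 to D18: not asked, so blank.
5. The fentanyl questions promised in Section C do not come, apart from the attitude items and conditional items in step 4 below.

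**Step 2. Ask whether the D13 skip does any work.** D15 to D18 already require fentfreq to show use. If D14 were asked of everyone, a person answering Never would pass over D15 to D18 without help from D13. The only thing the D13 rule adds is the loss of D14, and with it D15 to D18, for people who would have reported use.

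**Step 3. Set baseline beside follow-up.**

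| Content | Baseline | Follow-up |
|---|---|---|
| Past-month frequency | D14 (fentfreq), only after agreement with D13 | C13 (fentfreq_fu), everyone |
| Action on finding out | D18 (skill1), after D13 and then fentfreq | C18 (skill1_fu), no printed condition |

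The participant in step 1 has a blank at baseline and perhaps Every day at month 1. No change score exists. A summary of baseline frequency describes a selected group; the follow-up summary describes all attenders.

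**Step 4. Look for other baseline items that could fill the gap.**

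- Section C: the Other rows, and the free-text fields for the drug used or preferred most, could catch fentanyl if the participant names it.
- D26: preference for fentanyl, asked of everyone; it gives no frequency or timing.
- D46 to D47b: only people with a positive test strip in the past month.
- F17b and F17c: only people with an overdose in the past month, with prior knowledge asked only if fentanyl was suspected.

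None of these asks every knowing user for frequency, 3-day use and prior knowledge.

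**Step 5. Apply this to the urine result.** Compare the step 1 participant, who disagreed with D13, with one who answered Neutral because they did not know what was in their drugs. Both screen positive for fentanyl at baseline, and both have D14 to D18 blank. The first exposure was intentional and the second was not. The items designed to separate them (D15 for the three-day window, D16 for prior knowledge) were asked of neither.

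**The case against.** Several stronger readings are tempting, and the documents do not support them.

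- *Knowing users are recorded as non-users.* They are not. Never is a separate answer to D14, and nothing in either document says a blank is to be read as Never. The data are missing; a false zero would need an analyst to create it.
- *Fentanyl use is invisible at baseline for these people.* This goes too far, as step 4 shows. The notice deferring fentanyl appears only with the injection items, so a non-injecting user could name fentanyl in the open fields. The urine screen is also done whatever the answer to D13.
- *All knowing users are lost.* D13 has no time limit, so a knowing user who is confident of even one undisclosed exposure passes the gate. Eligibility also requires recent heroin, illicit stimulants, counterfeit pills or injecting, so use of non-injected fentanyl alone does not qualify.
- *A count can be given.* An assumed 10% to 40% not agreeing with D13 would be 0.10 × 550 = 55 to 0.40 × 550 = 220 people with D14 to D18 blank. That counts everyone who fails the gate, including non-users and people who are unsure. The documents give neither that share nor the share who are knowing users.
- *An Aim 3 modifier or an adjustment variable is missing.* The SAP lists "type, frequency, and route of drug use" for an aim it calls exploratory, and substance use patterns for adjustment. It does not name fentanyl frequency in either place. The loss reaches those analyses only if the team puts fentanyl use into them.
- *The treatment comparison is biased.* The rule is the same in both arms and comes before the intervention. The primary endpoint uses none of these items.

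It is also fair to say that the SAP has no rule for classing urine results by intent and no planned baseline-to-follow-up comparison of fentanyl use. What stands against the objection is that the protocol states the purpose of the urine screen and lists intentional use as a measure, and the form as printed cannot deliver either for this group.

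**Conclusion.** The flaw is real and limited. The skip after D13 leaves out some participants to whom D14 plainly applies, and D14 to D18 are the only general baseline items on frequency, recent use and prior knowledge of non-prescription fentanyl.

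There are two consequences. First, a positive baseline urine screen in a participant routed past these items cannot be classed as intentional or unintentional. Second, baseline fentfreq and skill1 are not comparable with C13 and C18. If skill1 is used as a behavioural-skills measure in Aim 2, where the first step looks at rate of change by arm, change cannot be computed for the people skipped.

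The number affected is unknown and may be small. The primary comparison, its power and the overdose endpoints are not affected. The conclusion assumes that the survey was programmed as printed.

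**What to change.** **Survey.** Delete the skip after D13 so that D14 is asked of every participant, as C13 is at follow-up, and let fentfreq alone gate D15 to D18. Two details should be settled at the same time:

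- C18 is printed with no condition, whereas D18 would still depend on fentfreq. Give both the same condition if skill1 is to be compared over time.
- D15 has no row for fentanyl bought as such, and nor does its follow-up counterpart C14. Tell interviewers to record it under Other at both.

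**Baselines already completed.** State in the SAP or data dictionary that D14 to D18, when skipped because of D13, are coded as not asked, never as Never. State also that a positive baseline urine screen in such a participant is not classed as unintentional exposure. Report how many participants were routed past D14, so that a reader can see how large the gap is.

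**Cost.** One branching rule is removed, and those now skipped have a minute or two more of interview. The downside is that baselines already collected cannot be recovered, and the baseline fentanyl data will mix participants asked under two routings, which should be flagged by date of change.
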